Marianne *et al* studied on 327 patients with chronic hepatitis C, each patient was scoring by METAVIR system, and the median value of LSM for F0-1, F2, F3 and F4 was 5.5 (4.1-7.1) kPa, 6.6 (4.8-9.6) kPa, 10.3 (7.6-12.9) kPa and 30.8 (16.3-48) kPa respectively; and the Area Under ROC (AUR) for F \geq 2, F \geq 3 and F=4 (METAVIR scoring system) was 0.79, 0.91 and 0.97 respectively. Therefore, the LSM varied significantly (P<0.0001) and was significantly related to the liver fibrosis (tau beta of Kendall, 0.55; P<0.0001).

A multi-center and large-sample comparison study between FibroScan and liver biopsy in the chronic hepatitis B patients in China also demonstrated that LSM had good diagnostic accordance rate to the pathological stages. The cut-off value of pathological stages \geq F4 was 17.5 kPa as, the sensitivity and specificity were 0.6 and 0.93 respectively; the cut-off value of pathological stages \geq F3 was 12.4kPa, the sensitivity and specificity were 0.58 and 0.95 respectively; the cut-off value of pathological stages=F2-F3 was 12.4kPa, the sensitivity and specificity were 0.73 and 0.90 respectively; and the cut-off value of pathological stages \geq F2 was 7.3kPa, the sensitivity and specificity were 0.66 and 0.83 respectively.

As stated in the “12th Five-year Plan for Medical Device Technological Industry” (the Ministry of Science and Technology), China will greatly support the research and development of new medical devices and promote the application of Chinese transient elastography system, FibroTouch, which was R&D by Tsing-Hua University independently with new algorithm. FibroTouch can rapidly determine the LSM in a non-invasive way and provide useful information for liver fibrosis staging.

As reported by a recent study on 214 CHB patients in Beijing Friendship Hospital underwent FibroScan testing and FibroTouch testing at the same time. FibroTouch and FibmScan have good consistency in the evaluation of the degree of liver fibrosis. FibroTouch has a significantly higher rate of effective detection (99% vs. 72%) and higher rate of successful detection than FibroScan (100% vs. 97%).

Due to FibroTouch is a new transient elastography system in marketing, there is no too much study on the correlation between FibroTouch and liver biopsy in diagnosis of liver fibrosis and cirrhosis.

II. Study Objective

(I) Primary Objective

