Use liver biopsy as “golden standard” for pathological staging, to evaluate the clinical values of FibroTouch for the non-invasive and quantitative diagnosis of liver fibrosis and cirrhosis in CHB patients.

(II) Secondary Objective

- ◆ Difference between FibroTouch and FibroScan in the rate of d successful detection
- ◆ Difference between FibroTouch and FibroScan in the determined values
- ◆ Correlation between determined values of FibroTouch and ultrasonic semi-quantitative scores
- ◆ Performance of FibroTouch.

- Positioning accuracy evaluated by investigators
- Image displaying ability evaluated by investigators
- Scanning speed evaluated by investigators
- Detecting and calculating speed evaluated by investigators

III. Study Goal

To determine the diagnostic accuracy, specificity and sensitivity of FibroTouch for liver fibrosis assessment in CHB patients.

IV. Study Type

It's a prospective and multicenter study.

V. Anticipated Total Cases

According to publications on FibroScan and liver biopsy examination, the mean sensitivity and specificity are 0.61 and 0.90 respectively for different stages (four pathological stages: $\geq F4$, $\geq F3$, $\geq F2$ and F0-F1). Assuming a similar sensitivity and specificity of FibroScan and FibroTouch, the lowest clinically acceptable sensitivity and specificity is 0.55

and 0.8 respectively, when $\alpha=0.05$ and power=80%, 423 cases are required based on sensitivity; total 529 cases are required based on the determination effectiveness=80%; 328 cases are required based on specificity; total 410 cases are required based on the determination effectiveness=80%. By considering the center assignment, ≥ 600 qualified cases are included to guarantee 500 final statistical cases; and ≥ 100 cases are required for S0+S1, S2, S3, S4 and liver cirrhosis (compensatory stage) respectively. For each stage, the case is assigned as equally as possible.

VI. Study Time

One year (from May 2014 to May 2015).

VII. Case Assignment System (via central registration system)

Subject No. is assigned through IWRS system. After the investigator logs in the system and fills in the pathological stages, this system will, according to the completed contents, automatically assign the sole subject No. for this subject.

VIII. Statistical Analysis

Peking University Clinical Research Institute

IX. Study Design

(I) Inclusion Criteria

1. Age: 18—65 years, both gender.
2. History of HBV or HBsAg positive > 6 months up to now.

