◆ By grouping according to the grading result via golden standard, the inter-group comparison is made on the FibroTouch determination results through the variance analysis or Wilcoxon rank-sum test, the correlation between two groups is tested through the Spearman correlation analysis, and the correlation coefficient (r) and 95% CI are calculated for two groups.

◆ By regarding the different grading results of golden standard as the judgment critical point, the curve of receiver operating characteristic (ROC) for elasticity value is constructed. The subjects are grouped by regarding the different determination results of elasticity value as the judgment critical point, the sensitivity/specificity is calculated according to the grading result of golden standard, the ROC curve is plotted through the X-axis of specificity, the Y-axis of sensitivity and the calculated result, and the area under curve and its 95% confidence interval are calculated. The critical value corresponding to whichever is greater for the result of sensitivity and specificity is regarded as the judgment critical point for FibroTouch determination value, and then the corresponding sensitivity, specificity, positive predicted value and negative predicted value are calculated.

Comparison of secondary objective: by statistically assuming the success rate of FibroTouch is non-inferior to that of Fibroscan, the critical value of non-inferiority is 10%; and by statistically assuming the determination result of FibroTouch is equivalent to that of Fibroscan, the critical value of equivalence is 1.5KPa.

In the above analysis, $P < 0.05$ indicates a significant difference.

(VIII) Data Management and Data Traceability

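### PPV and NPV are to be calculated with no stated prevalence from a sample recruited by biopsy stage, so they will not carry over to CHB patients with another stage mix

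*Combined protocol and SAP*

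**What the plan says.** Section V (Anticipated Total Cases) sets a minimum of 100 per stage group: "cases are required for S0+S1, S2, S3, S4 and liver cirrhosis (compensatory stage) respectively". It adds: "For each stage, the case is assigned as equally as possible". At least 600 "qualified cases are included to guarantee 500 final statistical cases". Section VII (Case Assignment System) issues the subject number by stage: "After the investigator logs in the system and fills in the pathological stages", the system assigns it.

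Section IX (VII), item 2, chooses a FibroTouch cut-off from the ROC curve for each biopsy threshold, and then "the corresponding sensitivity, specificity, positive predicted value and negative predicted value are calculated". Neither that section nor any other names a prevalence, an adjustment to a target stage mix, or a limit on how PPV and NPV may be read.

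The primary objective (II (I)) is the clinical value of FibroTouch for "the non-invasive and quantitative diagnosis of liver fibrosis and cirrhosis in CHB patients". The Study Goal (III) is narrower: "To determine the diagnostic accuracy, specificity and sensitivity of FibroTouch for liver fibrosis assessment in CHB patients". Section IX (VII) also says that a statistical analysis plan is still to be prepared.

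**The concern.** PPV and NPV are probabilities of disease given a test result, and they depend on how common the disease is among those tested. Here that frequency is largely a recruitment target. A 2×2 table from the study will give the PPV and NPV of a population with roughly equal numbers in each stage group, which need not resemble any clinic.

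A clinician reads these two figures as the chance that a positive or negative result is right. If they are published without a label, a clinic with fewer advanced cases would expect too much from a positive result and too little from a negative one. A clinic with more advanced cases would err the other way. The NPV at ≥S2 is the most exposed, because the design puts three quarters or more of the sample above that threshold.

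**Working it through.** **Figures in the plan.** The documents give no PPV, NPV or prevalence to reproduce. The planning values in Section V can be traced. The Background cites FibroScan accuracy in Chinese CHB patients for ≥F2 ("the sensitivity and specificity were 0.66 and 0.83 respectively"), for ≥F3 (0.58 and 0.95) and for F4 (0.60 and 0.93). The means are (0.66 + 0.58 + 0.60)/3 = 0.61 and (0.83 + 0.95 + 0.93)/3 = 0.90, which agree with Section V's 0.61 and 0.90. Section V also assumes that FibroTouch performs like FibroScan, so these inputs are in keeping with the plan's own basis.

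**Shares implied by the design (500 analysed).**
- Five equal groups of 100: ≥S2 400/500 = 80%; ≥S3 300/500 = 60%; S4 or cirrhosis 200/500 = 40%; cirrhosis alone 100/500 = 20%.
- Four equal groups of 125 (S4 and cirrhosis as one group): 375/500 = 75%; 250/500 = 50%; 125/500 = 25%.

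**Formulas.** With sensitivity Se, specificity Sp and prevalence p:
- PPV = Se·p / [Se·p + (1 − Sp)(1 − p)]
- NPV = Sp(1 − p) / [Sp(1 − p) + (1 − Se)p]

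**Worked case, ≥F2 (Se 0.66, Sp 0.83).**
- p = 0.80: PPV = 0.528/(0.528 + 0.034) = 0.94; NPV = 0.166/(0.166 + 0.272) = 0.38.
- p = 0.40: PPV = 0.264/(0.264 + 0.102) = 0.72; NPV = 0.498/(0.498 + 0.136) = 0.79.

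**All thresholds.**

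| Threshold (Se/Sp) | Prevalence | PPV | NPV |
|---|---|---|---|
| ≥F2 (0.66/0.83) | 80%, five groups | 0.94 | 0.38 |
| | 75%, four groups | 0.92 | 0.45 |
| | 40%, assumed | 0.72 | 0.79 |
| | 20%, assumed | 0.49 | 0.91 |
| ≥F3 (0.58/0.95) | 60%, five groups | 0.95 | 0.60 |
| | 50%, four groups | 0.92 | 0.69 |
| | 20%, assumed | 0.74 | 0.90 |
| F4 (0.60/0.93) | 40%, S4 or cirrhosis | 0.85 | 0.78 |
| | 25%, four groups | 0.74 | 0.87 |
| | 20%, cirrhosis alone | 0.68 | 0.90 |
| | 10%, assumed | 0.49 | 0.95 |

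**Does the result hang on Se = 0.66?** With Sp at 0.83 and Se varied over an assumed 0.55 to 0.80, the ≥F2 NPV is 0.32 to 0.51 at 80% prevalence and 0.73 to 0.86 at 40%. The ranges do not overlap.

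**Does accuracy itself move with the mix?** It can, because pooled Se and Sp average over the stages on each side of the cut-off. Take, purely as assumptions, test-positive rates at the ≥S3 cut-off of 5% (S0+S1), 25% (S2), 45% (S3) and 70% (S4 or cirrhosis).
- Five equal groups: Se = (0.45 + 2×0.70)/3 = 0.62; Sp = 1 − (0.05 + 0.25)/2 = 0.85.
- Assumed mix of 60:20:10:10: Se = (0.45 + 0.70)/2 = 0.58; Sp = 1 − (60×0.05 + 20×0.25)/80 = 0.90.
- At 20% prevalence, PPV/NPV is 0.51/0.90 with the first pair and 0.59/0.89 with the second.

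In this example the shift is smaller than the prevalence effect in the table, but not nil.

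**The case against.** **PPV and NPV are minor outputs.** The Study Goal and the sample size rest on sensitivity and specificity. PPV and NPV appear once and have no target, test or decision rule. This stands, and it limits the weight of the point.

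**The analysis plan is not yet written.** It could supply the prevalence or the label. That is so, but Section IX (VII) already prescribes the calculation, and nothing in the documents commits the later plan to either.

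**The quotas are floors.** A reader might infer that the design fixes prevalence at exactly 80%, 60% and 40%. The text does not support that: it gives minimums and an aim of equality, with no cap and no rule for closing a stage. With 600 enrolled in five groups of at least 100, the ≥S2 share could lie between 400/600 = 67% and 500/600 = 83%. If there are four groups and the minimums apply only at enrolment, 300 S0+S1 cases and 100 in each other group are possible. If all 100 losses then fell at ≥S2, the share would be 200/500 = 40%. Equal filling makes this unlikely, but the shares are targets. They still come from recruitment and do not estimate the stage mix in CHB patients.

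**The illustration holds accuracy fixed and maps F stages onto S stages.** Both are assumptions. Appendix 4 has no column for the S stages, so the mapping cannot be checked from the documents. The figures show how far predictive values can move; they do not forecast FibroTouch results.

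**Conclusion.** The point holds as a limited fault in a secondary output that should be fixed. Raw PPV and NPV from this sample will describe its recruited stage mix, and the plan neither says so nor offers values for any other mix. For ≥F2 the illustration moves from 0.94/0.38 at the five-group share, or 0.92/0.45 at the four-group share, to 0.72/0.79 at an assumed 40% and 0.49/0.91 at an assumed 20%.

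These sizes rest on three assumptions: F stages match S stages, FibroTouch accuracy equals the cited FibroScan accuracy, and accuracy stays fixed across mixes. All prevalences other than the design shares are also assumed.

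Two stronger conclusions might be inferred and are not supported. The first is that the study is invalid. Sensitivity and specificity are the stated goal, and the AUC is estimated alongside them. Recruiting by stage is compatible with estimating all three, although their pooled values also reflect the mix. The second is that PPV will be overstated and NPV understated in general. The documents give no natural stage distribution, so no direction can be claimed.

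**What to change.** In Section IX (VII), item 2, or in the analysis plan to be prepared:

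1. Report PPV and NPV at each cut-off by Bayes' formula over a stated prevalence range that includes the sample's own shares, for example 10% to 80%, extended if an achieved share falls outside it.
2. Label any raw PPV or NPV as specific to the study's stage mix.
3. Tabulate the test-positive rate in each biopsy stage at each cut-off, so that readers can apply another mix.

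Re-weighting sensitivity and specificity to assumed stage mixes is an optional sensitivity analysis; the documents give no mix to re-weight to, so any mix used must be stated as an assumption.

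The cost is one or two extra tables from data already collected, with no change to recruitment. Some figures will look less favourable.

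### The success-rate objective is a difference between devices, but only a 10% non-inferiority verdict is planned, with no estimate or confidence interval; the paired interval would supply both and allow a superiority reading at no alpha cost

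*Combined protocol and SAP*

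**What the plan says.** Section II (II), Secondary Objective, lists "Difference between FibroTouch and FibroScan in the rate of d successful detection". It names no direction.

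Section IX (VII), Statistical Analysis of Data, gives the matching analysis in one clause: "by statistically assuming the success rate of FibroTouch is non-inferior to that of Fibroscan, the critical value of non-inferiority is 10" per cent. It gives no superiority step, no confidence interval for the rate difference, no paired method, no sidedness and no reason for the margin. It closes with a general rule: "In the above analysis, $P < 0.05$ indicates a significant difference".

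The background cites a study of 214 patients with chronic hepatitis B examined with both devices: "FibroTouch has a significantly higher rate of effective detection (99% vs. 72%) and higher rate of successful detection than FibroScan (100% vs. 97" per cent).

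Section IX (III) has both devices used at the same site on the same day, so the data are paired. Item 5 requires 10 successful FibroTouch acquisitions with an IQR-to-median ratio of at most 0.3, and repetition until the result is reliable. Item 6 requires 10 effective FibroScan determinations. It allows the measurement site to be adjusted after a failure, but sets no reliability threshold and no repeat rule.

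**The concern.** The objective asks how the devices differ, and the planned test returns one bit: whether FibroTouch is worse by more than 10 points. When success rates lie near 97 to 100%, that bit is nearly certain in advance and is the same for an equal device and a better one. The general rule on P values makes this worse. A non-inferiority P value below 0.05 means not worse by more than the margin, yet the rule reads any such P value as a significant difference. A pass could therefore be reported as a difference that was never tested.

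What is at stake is modest. The data that decide non-inferiority also estimate the difference and can show whether it excludes zero. If this is not written down, the report may give only the weaker conclusion, or a superiority statement may be added after the results are known and look driven by them.

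**Working it through.** **The plan's own figures.** No sample size or power is given for the success-rate comparison. The only figure available to reproduce is the primary one in section V: "423 cases are required based on sensitivity", from an expected sensitivity of 0.61 and a lowest acceptable value of 0.55, with alpha 0.05 and power 80%. An exact one-sample binomial test at one-sided 0.05 reaches 80% power first at n = 423, and 423/0.80 = 528.75, which gives the stated 529. The two-sided normal approximation gives 534 instead of 423. The plan's alpha therefore appears to be one-sided, while section IX (VII) states no sidedness. The level for the success-rate comparison has to be stated.

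**Inputs.** n = 500 pairs (final statistical cases, section V); margin 10 points (section IX (VII)); 100% against 97% successful detection (background). The correlation of failures between devices is not given. Independence is assumed where needed, and a range is shown below.

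**Notation.** p10 is the probability that FibroTouch succeeds and FibroScan fails, p01 the reverse, d = p10 - p01, and SE = sqrt[(p10 + p01 - d²)/n].

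**Step 1: non-inferiority.** Power = Φ[(d + 0.10)/SE - 1.96].
- 97% vs 97%, independent: p10 = p01 = 0.97 × 0.03 = 0.0291; SE = sqrt(0.0582/500) = 0.0108; 0.10/0.0108 = 9.3; power about 100%.
- 100% vs 97%: p10 = 0.03, p01 = 0; SE = sqrt(0.0291/500) = 0.0076; 0.13/0.0076 = 17; power about 100%.
- FibroTouch truly worse, 92% vs 97%, independent: p10 = 0.0276, p01 = 0.0776; SE = sqrt(0.1027/500) = 0.0143; 0.05/0.0143 = 3.49; power 0.94.

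The verdict does not separate equal from better. It is usually the same for a device 5 points worse. Against 97%, the margin extends to 87%.

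**Step 2: the interval.** At 100% vs 97%, d ± 1.96 SE = 0.030 ± 0.015, that is 1.5 to 4.5 points. This needs no correlation assumption, because FibroTouch has no failures.

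**Step 3: superiority power** (exact McNemar test, two-sided 5%, n = 500).
- 100% vs 97%: all discordant pairs favour FibroTouch. Since 0.5⁵ = 0.031 and 0.5⁶ = 0.016, six are needed for one-sided 0.025. P(Bin(500, 0.03) ≥ 6) = 1 - 0.0025, or 99.7%.
- 99% vs 97%, independent: p10 = 0.0297, p01 = 0.0097; power 55%.
- 98% vs 97%, independent: p10 = 0.0294, p01 = 0.0194; power 12%.

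Range for the last two: if every FibroTouch failure were also a FibroScan failure (p01 = 0; p10 = 0.02 and 0.01), power would be P(Bin(500, 0.02) ≥ 6) = 93% and P(Bin(500, 0.01) ≥ 6) = 38%. If no patient failed on both (p10 = 0.03; p01 = 0.01 and 0.02), it would be 54% and 12%.

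**Step 4: alpha.** A lower limit above 0 is necessarily above -10 points, so superiority cannot be declared without non-inferiority. In 200,000 simulated trials of 500 pairs per scenario this never happened. With equal rates of 97%, superiority was declared in 2.6% of trials at a nominal one-sided 2.5%.

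**The case against.** FibroScan is the established device and FibroTouch the new one, so asking whether the newcomer is not materially worse on an operational endpoint is coherent. Non-inferiority is itself a question about the difference. A reader might infer that the planned test cannot answer the objective at all; the documents do not support that. The objective names no direction and promises no superiority, and the interval normally used to judge non-inferiority also estimates the difference. The gap is that this interval is not specified.

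A reader might also take the 99% against 72% in the background as proof that superiority is assured. Those are rates of effective detection, which the cited study reports separately from successful detection. The objective and the test concern successful detection, so 100% against 97% is the relevant pair, and it comes from one report of 214 patients. One FibroTouch failure per hundred lowers the power to about 55% under independence.

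Since superiority implies non-inferiority, a superiority reading made later would still be valid within this endpoint. What is lost by not planning it is credibility more than error control. This stands, and it keeps the point minor.

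The strongest objection concerns measurement. FibroTouch is repeated until reliable, and FibroScan has no written counterpart, so a superiority result could come from unequal rules. This stands too and makes a common rule a precondition. Because both sections already ask for 10 valid acquisitions, such a rule can be written without new procedures.

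Section IX (VII) also foresees a separate statistical analytical plan. More detail may have been intended, but the hypothesis and margin are already set here without the estimate.

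**Conclusion.** The point holds as a cheap improvement. The plan sets a difference as the objective and specifies only a non-inferiority verdict at 10%, which at about 500 pairs is close to certain for an equal device and a better one alike. It does not specify the paired estimate and interval that would answer the objective directly.

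Reading superiority from that interval after non-inferiority costs no alpha within this endpoint, provided that population, level and order are fixed. It does not settle multiplicity across the other secondary comparisons, such as the 1.5 kPa equivalence test. Superiority should be described as possible, not expected: power is 99.7% only if FibroTouch has essentially no failures, and about 55% or 12% at true rates of 99% or 98% against 97% with independent failures. These figures assume 500 pairs and a margin in percentage points.

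**What to change.** In section IX (VII), replace the success-rate clause with the following content:
- Report the paired difference in success rate, FibroTouch minus FibroScan, in all patients attempted on both devices, with a two-sided 95% confidence interval by a method for paired proportions.
- Declare non-inferiority if the lower limit is above -10 points and, only then, superiority if it is above 0. Report the estimate and interval in either case.
- Exempt this comparison from the general sentence on P values, so that a non-inferiority pass is not read as a difference.

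As a precondition, define success by one rule for both devices, for example 10 valid acquisitions obtained at the first examination, so that repetition on one device cannot create the difference. The denominator should not be limited to the 500 final statistical cases if these exclude failed measurements.

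The cost is a few sentences and no extra patients. The real work is to write the common definition and apply it to both devices, including a record of whether success came at the first examination if the case report form does not already capture it.
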